### A. Specific Aims

The long term objective of this study is to establish objective measurements of musculoskeletal changes that occur in response to osteopathic manipulative treatment (OMT). Many patients who suffer from low back pain (LBP) receive OMT to the lumbar, pelvic, sacral, and lower extremity body regions that helps resolve or manage their pain. The indication for OMT in a patient suffering from LBP is the presence of somatic dysfunction found during the physical examination. Somatic dysfunction is diagnosed when one or more of the following physical findings are present: tenderness, asymmetry, restricted range of motion, and tissue texture abnormalities. OMT is performed to specifically target these physical findings, after which the patient is reassessed for a reduction or resolution of the findings. In the clinical setting the assessment and reassessment of somatic dysfunction is performed using palpatory examination. Because palpatory findings commonly demonstrate poor interexaminer reliability, the proposed study will use ultrasound to establish pre- and postOMT musculoskeletal measurements of the relative asymmetry between the participants' pelvic and sacral bony landmarks. The investigators will use a control group to compare the changes in the pre and post OMT measurements to participants who have not received OMT. If ultrasonography is able to detect a significant change in the relative asymmetry between the pelvis and sacrum, then ultrasound may be useful for assessing and quantifying outcomes for OMT in a variety of body regions such as spine, shoulders, and knees. To determine if ultrasound is a reliable objective measure to assess OMT outcomes in LBP patients the following specific aims are proposed:

- Determine if ultrasound measurements of sacral landmarks are stable over 30 minutes in untreated participants.
- Determine the extent to which OMT affects the relative asymmetry between the pelvic and sacral landmarks as measured by ultrasonography.
- Determine if ultrasound measurements of sacral base asymmetry agree with palpatory assessment.

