## Preliminary Data

As part of a study investigating the feasibility of integrating ultrasound into an OMM curriculum, 247 students assessed the sacral base asymmetry of another student using US. They measured SPSIS and SSB on the right and left sides, then calculated the SSD as (SSB) - (SPSIS) = (SSD). The results are shown in Table 1. The calculated SSD demonstrated a wide range of depths (0 to 4.03 cm). The sacral sulcus depth difference (SSDD) between the right and left sides also demonstrated a wide range (-2.01 to 2.52 cm). Negative SSDD values indicated that the right sacral sulcus depth was shallower than the left and positive values indicate that the right sacral sulcus was deeper than the left, although these differences were not statistically significant.

Table 1: Student measurements of sacral base landmarks (N=247).

	Left SPSIS (cm)	Left SSB (cm)	Right SPSIS (cm)	Right SSB (cm)	Left SSD (cm)	Right SSD (cm)	SSDD (cm)
Maximum	6.33	8.24	4.94	8.29	3.65	4.03	2.52
Minimum	0.49	1.48	0.37	1.67	0.00	0.33	-2.01
Average	1.72	3.61	1.64	3.62	1.88	1.98	0.10
STDev	0.81	0.96	0.77	0.97	0.59	0.63	0.57

Abbreviations: SPSIS, distance from skin to posterior superior iliac spine (PSIS); SSB, distance from skin to sacral base (SSB); SSD, sacral sulci depth calculated as (SSB) - (SPSIS) = (SSD); SSDD, sacral sulcus depth difference between right and left SSD.

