## Data analysis

Power calculations performed on preliminary SSDD data suggested that recruiting 38 participants would allow us to detect mean difference of  $\pm 0.5$  cm in the two treatment groups at pre-post treatment analysis at 0.05 significance level with 80% power. We plan to recruit 40 participants total (20 in each group). While the students, who collected the preliminary data, were not expert ultrasonographers, the quantity of data allows for an estimation of the likely range of measurements that will be seen in the proposed study. Descriptive statistics such as means, ranges, and standard deviations (SD) for continuous variables and frequency and percent will be used to summarize the categorical data. Two sample *t*-tests will be used to compare mean age and BMI across groups.

Correlations between BMI and US measurements will be calculated for each landmark (SPSIS, SSB, SSD). Absolute asymmetry between left and right landmark measurements will be calculated as follows:

$$\text{absolute asymmetry} = |\text{landmark}_{\text{left}} - \text{landmark}_{\text{right}}|$$

To determine if absolute asymmetry increased, decreased, or stayed the same after intervention, direction of change in asymmetry will be calculated as follows:

$$\begin{aligned}\text{direction of change in asymmetry} &= |2^{\text{nd}} \text{ US landmark}_{\text{left}} - 2^{\text{nd}} \text{ US landmark}_{\text{right}}| >, <, \text{ or} \\ &= |1^{\text{st}} \text{ US landmark}_{\text{left}} - 1^{\text{st}} \text{ US landmark}_{\text{right}}|\end{aligned}$$

To account for total change in measurements at both left and right landmarks between the first and second US measurements, total change in asymmetry between first and second US assessments will be calculated as follows:

$$\text{total change in asymmetry} = |(1^{\text{st}} \text{ US landmark}_{\text{left}} - 1^{\text{st}} \text{ US landmark}_{\text{right}}) - (2^{\text{nd}} \text{ US landmark}_{\text{left}} - 2^{\text{nd}} \text{ US landmark}_{\text{right}})|$$

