The Fisher exact test is to be used to test associations between group and direction of change in asymmetry at each landmark. Multiple linear regression models will be built to compare mean absolute asymmetry for each landmark measured during the first US assessment between groups while controlling for demographic characteristics, date of last pain, and frequency of pain. Similar multiple linear regression models will be built to compare mean total change in asymmetry from first to second US assessment between groups for each landmark between groups.

Mean absolute asymmetry at the first and second US assessments and mean total change in asymmetry for seated control and OMT groups will be compared using a 2-sample t test. To compare qualitative palpitory assessment of SBP and SSD with quantitative US measurements, US measurement of landmark position will be first converted to a qualitative assessment as follows:

- right anterior SBP or deep SSD = right US measurement > left US measurement
- right posterior SBP or shallow SSD = right US measurement < left landmark measurement
- equal SBP or SSD = right US measurement = left US measurement

To compare agreement between qualitative palpitory and US assessments of SBP and SSD,  $\kappa$  and associated 95% CIs will be calculated. Values less than or equal to 0 indicated no agreement; 0.01 to 0.20, none to slight; 0.21 to 0.40, fair; 0.41 to 0.60, moderate; 0.61 to 0.80, substantial; and 0.81 to 1.00, almost perfect agreement.

To determine if US localization of landmarks at the sacral base was reliable, intraclass correlation coefficients (ICC) and associated 95% CIs will be calculated for US measurements from the first to second US assessment for each landmark. For ICC, 0.7 to 0.8 was considered good; 0.8 to 0.9, very good; and 0.9 to 1.0, excellent.  $P \leq 0.05$  was considered significant. Data analysis will be performed using SAS statistical software version 9.4 (SAS Institute, Inc.).

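### The only measures of the size of the OMT effect are means of absolute values, so reading error makes the between-arm difference too small; a signed regression should be added beside them

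*Combined protocol and SAP*

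**What the plan says.** Under A. Specific Aims, the second aim is to "Determine the extent to which OMT affects the relative asymmetry between the pelvic and sacral landmarks as measured by ultrasonography". That asks for an amount, not only for a yes or no.

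The Data analysis section defines two outcomes that carry an amount. For the first, "Absolute asymmetry between left and right landmark measurements will be calculated as follows": the modulus of left minus right. The second, total change, is the modulus of the change in left minus right from the first scan to the second. The section then compares "Mean absolute asymmetry at the first and second US assessments and mean total change in asymmetry for seated control and OMT groups" by two-sample t test. Total change is also compared by multiple regression. A third outcome records whether the modulus rose, fell or stayed the same and is compared by Fisher exact test. It keeps direction but drops size.

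No signed difference is compared between arms, and no step removes reading error from an estimate. The preliminary data, by contrast, are signed: "Negative SSDD values indicated that the right sacral sulcus depth was shallower than the left".

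**The concern.** The mean of an absolute value depends on scatter as well as on the quantity of interest. A participant made perfectly symmetric still shows a positive left-right modulus at the second scan, because each reading has error. An untreated participant in whom nothing moved still shows a positive total change.

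This floor does not drop out of the between-arm difference. Error adds most to the mean modulus where the true value is smallest. For absolute asymmetry that is the OMT arm, if OMT works. For total change it is the control arm. In both cases the gap between arms shrinks, so the trial could report an effect materially smaller than the one that occurred.

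**Working it through.** **The plan's own figure.** The Data analysis section states that "recruiting 38 participants would allow us to detect mean difference of" 0.5 cm "at 0.05 significance level with 80% power". With the Table 1 SD of 0.57 cm, the two-sided normal formula gives 2 × (1.960 + 0.842)² × 0.57² / 0.5² = 20.4, so 21 per arm or 42 in total (44 with the t distribution), not 38. That mismatch is a separate matter. What counts here is that the calculation used signed SSDD and supplies no reading-error SD.

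**Inputs.** SSDD mean 0.10 and SD 0.57 cm (Table 1, Preliminary Data); 20 per arm (Data analysis). Assumed: normality, and reliability R of the measured left-right difference between 0.6 and 0.9. The documents give no value for R. The lowest labelled ICC band in the Data analysis section starts at 0.7.

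**Model.** First-scan difference D1 = T + e1; second-scan difference D2 = kT + e2. True asymmetry T has mean 0.10 and variance 0.57²R. Each error has variance 0.57²(1−R). Controls have k = 1; a true halving by OMT is k = 0.5.

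**Formula.** For a normal variable with mean m and SD s, the mean modulus is F(m, s) = s√(2/π)·exp(−m²/2s²) + m[1 − 2Φ(−m/s)].

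**Worked case, R = 0.8, true halving.** The true mean reduction is 0.5 × F(0.10, 0.510) = 0.207 cm.
- Absolute asymmetry at scan 2: control F(0.10, 0.57) = 0.462; OMT F(0.05, 0.57√(0.25×0.8 + 0.2)) = 0.290. The difference is 0.171 before rounding, and 0.171/0.207 = 83%.
- Total change: control F(0, 0.57√(2×0.2)) = 0.288, although nothing moved; OMT F(0.05, 0.57√(0.25×0.8 + 0.4)) = 0.355. The gap is 0.067, and 0.067/0.207 = 32%.

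**Share of a true halving recovered, and power at 20 per arm** (simulation, 20,000 trials; sex not simulated):

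| R | Recovered, absolute SSDD | Recovered, total change | Power, absolute SSDD | Power, total change | Power, signed interaction |
|---|---|---|---|---|---|
| 0.6 | 68% | 21% | 22% | 6% | 22% |
| 0.7 | 75% | 26% | 31% | 8% | 35% |
| 0.8 | 83% | 32% | 44% | 13% | 56% |
| 0.9 | 91% | 44% | 59% | 32% | 89% |

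If OMT removed all true asymmetry, recovery would be 48% to 72% on absolute SSDD and 38% to 64% on total change.

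**Loss of sign.** A true change of −0.5T and one of +0.5T give the same distribution of total change. A halving and a 1.5-fold worsening therefore have the same mean.

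**Type I error.** With no OMT effect and equal error in both arms, both t tests reject in about 5% of trials. If second-scan error SD were 1.25 times larger in the OMT arm, total change would reject in about 7% to 8%; at 1.5 times, about 15%.

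**Why a signed regression avoids the floor.** The slope of D2 on D1 is R in controls and kR under OMT. The ratio is k, so 1 minus the ratio is the fraction removed. First-scan error cancels in the ratio, and second-scan error that is independent of D1 does not bias either slope. In simulation the median estimate for a halving is 0.50 at each R. The interaction test rejects in about 5% of no-effect trials even with 1.5 times the error in one arm.

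**The case against.** **The size is assumed.** This stands. R is not in the documents, and the 0.57 cm SD comes from students whom the plan itself calls non-expert. The trial uses one highly experienced examiner. At R = 0.95 a halving would be recovered at about 95%. The direction of the bias does not depend on R.

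**The plan already guards against reading error.** It has one blinded examiner, ink marks, consistent pressure, ICCs and a control arm for stability. These reduce error or describe it; none corrects the estimate. The ICCs are planned per landmark, and the reliability of a left-right difference need not equal that of a single depth.

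**The proposed model was tested on data that suit it.** This stands too, and it limits the fix. The slope ratio returns the true fraction only if OMT acts roughly proportionally, while technique is left to the treating physician. At R = 0.8, if OMT took up to 0.2 cm off each asymmetry, mean true asymmetry would fall by 41% and the slope would report 30%. If OMT cleared only asymmetries above 0.5 cm, the figures would be 63% and 82%. If OMT moved landmarks regardless of first-scan asymmetry (SD 0.4 to 0.6 cm), total change would detect it in 34% to 72% of trials and the interaction in 5%. The signed model should therefore not replace the planned tests.

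**Stronger readings.** A reader might infer that the t tests are invalid, or that unequal scatter will pass as an OMT effect. The documents do not support either. With equal scatter the 5% level holds. Nothing shows that scatter differs by arm, although handling one arm and not the other means that it is not excluded. A reader might also take total change as a measure of asymmetry removed. It is unsigned and cannot measure that.

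**Conclusion.** The concern holds as a bias in the estimated size of the effect, not as a fault in the tests under equal scatter. Both magnitude outcomes carry a reading-error floor that shrinks the between-arm difference when OMT works. On Table 1 values with assumed reliability of 0.6 to 0.9, a true halving is recovered at about 68% to 91% on absolute SSDD and 21% to 44% on total change. Excess rejection on total change would arise only if second-scan error were larger in the OMT arm. These figures assume normal differences, independent errors, a proportional effect, and participants who resemble the Table 1 students in spread. The same mechanism applies to the other landmarks, but its size there was not computed.

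**What to change.** Keep the planned comparisons of absolute asymmetry and total change. For each landmark, add a prespecified regression of signed (L2−R2) on (L1−R1), group, group × (L1−R1) and sex. Use the interaction as the test of shrinkage toward symmetry. Report the control slope, the OMT slope and 1 minus their ratio, each with a 95% CI from a bootstrap over participants. State in the interpretation that the absolute-value means include a reading-error floor.

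The cost is SAP wording and one more regression per landmark on readings already taken. The downsides should be written into the plan:
- The fraction assumes a roughly proportional effect.
- It is imprecise at 20 per arm. For a true halving, the central 95% of estimates runs from about 0.06 to 0.80 at R = 0.8, about −0.2 to 0.9 at R = 0.7, and about −0.7 to 1.1 at R = 0.6.
- It does not detect movement unrelated to first-scan asymmetry. Total change should stay a planned comparison for that purpose.

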#### D. Research Design and Methods

This prospective, randomized, controlled trial is proposed to investigate the effect of OMT on sacral base asymmetry as assessed by US. The study will be conducted over the course of two months. Forty men and women ages 20 to 55 years with at least one or more episodes of LBP in the past two weeks will be randomly assigned into one of two groups – control or OMT groups. Twenty participants will be assigned to each group. The study will begin recruitment in July 2016 pending institutional review board approval. Participants will be recruited from the surrounding Kirksville area. Individuals with prior spinal surgery, fractures, or known congenital anomalies of the lumbar vertebra and sacrum will be excluded. Individuals who cannot lie prone for 30 minutes, or who cannot tolerate OMT will be excluded. Subjects will be randomly assigned into two groups, control or OMT using a random number generator. Males and females will be randomized separately to ensure equal distribution into the two study groups. Demographics including sex, age, and body mass index (BMI) will be collected on all participants.

All participants will receive an initial palpatory assessment of the sacral base asymmetry and then an initial ultrasound evaluation of sacral base asymmetry. After the ultrasound assessment, the control group will wait in another room for approximately 30 minutes. Participants in the OMT group will receive OMT to address sacral base asymmetry after the initial ultrasound assessment. Following the treatment period for the OMT group, all subjects will receive a second ultrasound assessment of sacral base asymmetry. The ultrasonographer will be blinded on whether the subject received an OMT or not.

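### Sex is the randomisation stratum, but second-scan absolute asymmetry is compared between groups only by a t test that leaves sex out; adding it costs almost nothing and may recover some precision

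*Combined protocol and SAP*

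**What the plan says.** Section D (Research Design and Methods) makes sex the stratum: "Males and females will be randomized separately to ensure equal distribution into the two study groups". The mechanism given is "Subjects will be randomly assigned into two groups, control or OMT using a random number generator", and the target is 1:1: "Twenty participants will be assigned to each group". Blocking within sex is not described. The same section lists what is recorded: "Demographics including sex, age, and body mass index (BMI) will be collected on all participants".

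The Data analysis section then plans two kinds of comparison of group means, for each landmark:

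- **Regression.** First-scan absolute asymmetry is compared "between groups while controlling for demographic characteristics, date of last pain, and frequency of pain". For the change outcome, "Similar multiple linear regression models will be built to compare mean total change in asymmetry from first to second US assessment between groups".
- **Unadjusted test.** The means of absolute asymmetry at each scan and of total change "for seated control and OMT groups will be compared using a 2-sample t test".

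Putting the two lists together:

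| Outcome | Adjusted regression | Unadjusted t test |
|---|---|---|
| First-scan absolute asymmetry | yes | yes |
| Second-scan absolute asymmetry | none named | yes |
| Total change in asymmetry | yes | yes |

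The Fisher exact test uses the second scan only through the direction of change, so it does not compare means.

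**The concern.** When randomisation balances a factor across arms, that factor's contribution to the group difference is largely removed by design. A t test that leaves the factor out still counts its variance as noise. If the factor is prognostic, the reported standard error is then larger than the true sampling error of the difference, and the test rejects less often than it should.

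Here the gap falls in an odd place. The pre-treatment comparison is adjusted, although any group difference there is due to chance. The post-treatment comparison of absolute asymmetry, which bears on the treatment effect, is not. With 40 participants there is little precision to spare. A smaller matter is that total change is to be tested both with and without adjustment, and the plan does not say which result leads.

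**Working it through.** **Inputs.** From the Data analysis section: difference 0.5 cm, significance level 0.05 (two-sided assumed), power 80%, stated need 38, planned 40 (20 per arm). From Table 1 under Preliminary Data: SD 0.57 cm for SSDD, the right-left difference in sulcus depth. This is the SD of a signed difference at one time point, not of an absolute asymmetry, so every power figure below is illustrative. Not in the documents: R², the share of variance in absolute asymmetry explained by sex. It is assumed over a range, with 10 men and 10 women per arm.

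**Step 1. The plan's own figure.** n per arm = 2(1.96 + 0.842)² × 0.57² / 0.5² = 20.4, so 21 per arm and 42 in total. The exact t calculation gives 21.4, so 22 per arm and 44 in total. The stated 38 is not reproduced from these inputs. That is a separate matter and the present point does not depend on it. At 20 per arm, power is 79.2% (normal approximation) or 77.1% (t test).

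**Step 2. Standard errors.** With total SD 0.57 and n = 20 per arm, the t test's standard error is 0.57 × √(2/20) = 0.180 cm. With sex balanced and in the model, it is 0.180 × √(1 − R²). The ratio of the two is 1/√(1 − R²).

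**Step 3. Type I error and power.** Simulation of 40,000 trials per setting, total SD held at 0.57 cm and true difference 0.5 cm; the t test is compared with a linear model containing group and sex.

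| Assumed R² | SE ratio | t test type I error | Power, t test | Power, group + sex | Power forgone (points) |
|---|---|---|---|---|---|
| 0 | 1.00 | 5.1% | 77.1% | 77.0% | about 0 |
| 0.02 | 1.01 | 4.8% | 77.5% | 78.0% | 0.5 |
| 0.05 | 1.03 | 4.3% | 78.1% | 79.6% | 1.5 |
| 0.10 | 1.05 | 3.9% | 78.1% | 81.3% | 3 |
| 0.20 | 1.12 | 2.9% | 79.4% | 85.7% | 6 |

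The t test's own power does not fall as R² rises. What is lost is the gain that adjustment would have given.

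**Step 4. How large a sex effect each R² implies.** With equal numbers of each sex, the male-female difference in means is 2 × SD × √R². At SD 0.57 and R² = 0.10 this is 2 × 0.57 × 0.316 = 0.36 cm. On the absolute scale, if SSDD is taken as normal with Table 1's mean of 0.10 and SD of 0.57, absolute SSDD has mean about 0.46 and SD about 0.35 cm. R² = 0.10 then needs sex means of about 0.35 and 0.57 cm, and R² = 0.20 about 0.31 and 0.62 cm. The documents report no such difference.

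**Step 5. The first scan as a covariate.** Adjusting for first-scan absolute asymmetry multiplies the residual SD by √(1 − r²), where r is the correlation between scans (assumed, not given). At r = 0.5 the SD becomes 0.57 × 0.866 = 0.494 and power rises from about 78% to about 87%. At r = 0.7 it reaches about 96%; at r = 0.3 the gain is about 3 points. Unless the correlation is weak, this covariate matters more than sex.

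**The case against.** The strongest reply is that nothing in the documents shows sex to be related to the outcome. The outcome is the absolute left-right difference, so a sex difference in depth common to both sides cancels. At R² of 0.02 or less the loss is under one power point. This stands, and it is why the point is conditional.

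Second, a reader might infer that the t test's true error rate is below 5%. That needs balance within sex. Section D aims for equal distribution but names only separate randomisation and a random number generator. With simple randomisation inside each sex, simulated type I error stays at about 4.5% to 5.2% for R² from 0 to 0.30, so the test is valid over repeated randomisations and adjustment only improves precision. In neither case are false positives inflated.

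Third, a reader might infer a fall in power from 79% to 66% at R² = 0.30. That comes from fixing the effect at 0.9 residual SDs and adding sex variance on top. The plan's SD of 0.57 cm is a total SD with no sex adjustment. Holding it fixed, the t test has 77.1% power at R² = 0 and 80.5% at R² = 0.30, so it loses nothing against the plan.

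Fourth, first-scan asymmetry and total change already have adjusted regressions, so it would be wrong to say that the plan ignores sex throughout. Showing an unadjusted result beside an adjusted one is also common practice; having both for total change is not an error, provided that one is named as the main analysis.

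What survives is narrower: the single comparison of second-scan means omits the factor used to randomise, and there is almost no cost to including it.

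**Conclusion.** The point holds for one outcome. Second-scan absolute asymmetry is compared between groups only by an unadjusted t test, although sex is the randomisation stratum and the other two outcomes have demographic-adjusted models. The direction is clear: if sex is prognostic and balanced, omission makes the standard error too wide and the test conservative. The size is not known. Under the stated assumptions (total SD 0.57 cm borrowed from signed SSDD, 0.5 cm difference, 20 per arm, sex balanced), the power forgone runs from nothing at R² = 0 to about 6 points at R² = 0.20, and the sex differences needed for the upper end look large beside Table 1. This is a cheap gain in precision and a match of analysis to design, not a threat to validity. The documents do not support saying that power is certainly lost.

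**What to change.** In the Data analysis section:

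1. Replace the 2-sample t test of second-scan absolute asymmetry, for each landmark, with a linear model containing group, sex and first-scan absolute asymmetry. Report the adjusted group difference with its 95% CI.
2. For total change, name the planned regression as the main analysis and state explicitly that sex is among its covariates. The unadjusted t test may stay as supportive.

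The cost is SAP wording and one or two degrees of freedom. Sex and the first scan are already recorded on every participant, so no new data are needed. At R² = 0, including sex costs about 0.1 power point.

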## Ultrasound Assessment

All participants will receive two ultrasound assessments evaluating sacral base asymmetry: an initial ultrasound assessment after the palpatory assessment, then a second ultrasound assessment after the treatment period. Ultrasound assessment will include the ultrasound imaging of the participants in the prone position during which an experienced ultrasonographer, who is blinded to the participant group assignment, will measure the depth from the skin to the PSIS (SPSIS) and the depth from the skin to the sacral sulcus base (SSB) on the right and left sides before and after the treatment period as illustrated in Figure 2. For each measurement, the ultrasound transducer will be placed directly over the landmark and consistent contact pressure will be used. The skin surface over the measurement locations will be marked with waterproof ink to ensure consistency in measurement locations between the first and second ultrasound assessments. The sacral sulcus depth (SSD) will be calculated from the two ultrasound measurements as  $(SSD) = (SSB) - (SPSIS)$ . The measurements will be compared before and after the intervention period. For comparison of the palpatory assessment of sacral base asymmetry to the ultrasound measurements, the larger SSB measurement will be considered the anterior sacral base, the smaller SSB will be considered the posterior sacral base, the greater SSD will be considered the deep sacral sulcus, and the lesser SSD will be considered the shallow sacral sulcus.

[figure not shown]
[figure not shown]

Figure 2. (A) Sacral base depth (SBD) will be measured as the distance between the skin and the sacral base position. Posterior superior iliac spine (PSIS) depth will be measured as the distance between the skin and the PSIS (SPSIS). Sacral sulcus depth (SSD) is calculated as  $(SSB) - (SPSIS) = (SSD)$ . (B) Ultrasound image illustrating the measured distance between the skin and the sacral base position, the distance between the skin, and the PSIS and the SSD.

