### Potential Limitations

The primary limitation to the ultrasound measurements is maintaining consistency in location of the initial and second ultrasound measurements. This limitation will be addressed by using a single, highly experienced ultrasound examiner. To ensure that the ultrasound measurements are made at the exact same locations during the initial and second ultrasound assessments on an individual participant, the

ultrasound examiner will mark the skin overlying the measurement locations using waterproof ink. The use of multiple types of OMT techniques in this study may introduce some potential treatment bias; however multiple techniques are typically used in on a single patient in a clinical setting. Future studies could assess the efficacy of individual techniques to improve asymmetry. The control group will be used to evaluate whether the ultrasound sacral measurements are stable over a period of time. To determine if participant sex, age, or BMI affect the reliability of the ultrasound or palpitory assessments, additional analyses may be run to assess if participant sex, age, or BMI confound the percent agreement between the two assessments.

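### The first-to-second-scan ICC is labelled a test of landmark localization, but at ink-marked sites it mainly shows same-examiner repeatability of depth readings, and it is not limited to untreated participants

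*Combined protocol and SAP*

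**What the plan says.** The Data analysis section gives the purpose of the ICC as "To determine if US localization of landmarks at the sacral base was reliable". The ICC and its 95% CI "will be calculated for US measurements from the first to second US assessment for each landmark". No study group is named. The result is graded on a fixed scale: "For ICC, 0.7 to 0.8 was considered good; 0.8 to 0.9, very good; and 0.9 to 1.0, excellent".

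Two other sections describe how the second scan is sited. Under Ultrasound Assessment, "The skin surface over the measurement locations will be marked with waterproof ink to ensure consistency in measurement locations". Under Potential Limitations the aim is put more strongly: "To ensure that the ultrasound measurements are made at the exact same locations during the initial and second ultrasound assessments on an individual participant". Whoever scans also makes the ink marks, and that section says that one experienced examiner does all the scanning.

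The first specific aim asks whether the measurements are stable over 30 minutes in people who were not treated. Potential Limitations likewise gives the control group the task of showing stability.

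**The concern.** The design holds the measurement site fixed between scans, and the analysis then offers the agreement between those scans as evidence that the site can be found reliably. If the first scan is off target, the mark takes the second scan to the same wrong place. The two depths agree, and the ICC looks good for a reason unrelated to localization.

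This matters because locating landmarks is part of the study's rationale. The Background sets palpation aside partly because examiners often misidentify bony landmarks, and the Specific Aims ask whether ultrasound is a reliable objective measure that might be extended to other body regions. A high ICC reported under the planned label would appear to answer a question that the design tests only in part.

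A second problem concerns who enters the ICC. If both arms are pooled, any real change produced by treatment is treated as disagreement between scans.

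**Working it through.** The plan gives no expected ICC and no localization error, so there is no figure to reproduce. The check has four steps.

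**1. What is repeated at the second scan**

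| Step | Repeated? | Basis |
|---|---|---|
| Finding the skin site | Largely not; the ink mark is reused | Ultrasound Assessment; Potential Limitations |
| Placing the probe, identifying bone in the image, reading the depth | Yes | Ultrasound Assessment |
| Search for the landmark without marks | Not described | – |
| Second examiner | No; a single examiner | Potential Limitations |

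**2. What this does to the ICC**

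Split the variance of one depth reading into between-person (B), site localization (L) and residual reading error (R).

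- Site reused: L is common to both scans, so ICC = (B + L) / (B + L + R).
- Site found afresh: L differs between scans, so ICC = B / (B + L + R).

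For a given total variance and R, the first expression does not change with the size of L. The second falls as L grows. This model treats site error as wholly shared, which is the limiting case. To the extent that the probe is not returned exactly to the mark, some of L does enter the planned ICC.

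**3. Illustration for sacral sulcus depth (SSD)**

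Inputs:
- SD 0.61 cm, the midpoint of 0.59 (left) and 0.63 (right) in Table 1, Preliminary Data. These are student measurements.
- Marked-site ICC 0.90 (assumed).
- Localization SD 0.1, 0.2 or 0.3 cm (assumed). It is a single net error for SSD, although SSD combines two separately located landmarks.

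Total variance = 0.61² = 0.3721. Shared part B + L = 0.90 × 0.3721 = 0.3349. Localization variance already sits inside this part, so it is subtracted to obtain B:

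| Localization SD (cm) | L | B = 0.3349 − L | ICC if re-localized = B / 0.3721 | Band in the plan |
|---|---|---|---|---|
| 0.1 | 0.01 | 0.3249 | 0.87 | very good |
| 0.2 | 0.04 | 0.2949 | 0.79 | good |
| 0.3 | 0.09 | 0.2449 | 0.66 | below the lowest band |

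In all three rows the planned ICC would be 0.90, at the lower edge of the top band.

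**4. Who enters the ICC, and the price of restricting it**

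The plan names no group, so as written the ICC could include all 40 participants, 20 of them treated between scans. In the treated arm, true change adds to the within-person difference and is counted as error.

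For the precision cost, take a one-way ICC of 0.90 with two readings per person. The F ratio is (1 + 0.90) / (1 − 0.90) = 19. The limits are (F* − 1) / (F* + 1), where F* is 19 divided by, or multiplied by, the 97.5% F quantile with the matching degrees of freedom.

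- n = 20: F* = 19 / 2.482 = 7.65 and 19 × 2.509 = 47.7, giving 0.77 to 0.96.
- n = 40: F* = 19 / 1.881 = 10.1 and 19 × 1.885 = 35.8, giving 0.82 to 0.95.

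**The case against.** Localization by ultrasound can fairly be read as identifying the bony landmark on the image, and that step is repeated. Controls wait in another room, so they have to be positioned prone again. A skin mark does not fix the probe angle or the position of skin over bone, and the plan's wording about identical sites states an aim rather than zero error. This stands. A reader might infer that localization error cannot enter the ICC at all, or that the landmarks are never located again. The documents do not support either reading: the search for the skin site is largely removed, and the rest of the process is redone.

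It is also true that the plan discloses the marks and the single examiner, and that the ICC sentence claims nothing about other examiners or about use without marks. The ICC feeds neither the group comparisons nor the power calculation, and marking is sensible for a before-and-after measurement. All of this limits the consequence. It does not justify the stated purpose, because disclosure in one section does not change what the analysis section says the ICC will determine.

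Finally, the figures in the illustration are assumed. They show the direction and a possible scale. They are not an estimate for this study.

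**Conclusion.** The point holds as a mismatch between label and design. As planned, the ICC measures same-examiner repeatability of depth readings at pre-marked sites. It tests at most part of localization error, because a site error made at the first scan is shared by the second. The size of any overstatement is unknown. The values of 0.87, 0.79 and 0.66 rest on an SSD SD of 0.61 cm, a marked-site ICC of 0.90, localization SDs of 0.1 to 0.3 cm already contained in the observed variance, and site error fully shared between scans.

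The missing group restriction is a separate part of the same sentence's problem. It conflicts with the first specific aim and with Potential Limitations, both of which place stability in the untreated group.

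This is a minor, inexpensive correction. A reader might infer that the ink marks are a design fault or that the treatment comparison is compromised. Nothing here supports that.

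**What to change.** Keep the ink marks and change the ICC paragraph in the Data analysis section:

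1. Restate the objective as same-examiner repeatability of depth readings at pre-marked sites over about 30 minutes.
2. Compute the primary ICC in the control arm. The all-participant ICC may be shown as secondary, with a note that it includes any change after treatment.
3. State that the ICC does not establish how reliably the landmarks can be located independently.

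This needs no extra scan, visit or participant, but it is more than a change of wording because the primary ICC moves from 40 to 20 participants. At an ICC of 0.90 the 95% CI widens from about 0.82–0.95 to about 0.77–0.96. The other cost is a narrower reliability claim.
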